4. OBJECTIVES AND OUTCOME MEASURES/ENDPOINTS

Objectives	Outcome Measures/Endpoints

Primary Objective
 
To confirm the clinical benefit of fluciclovine (¹⁸F) PET/CT in affecting management decisions in patients with BCR being considered for radical salvage treatment (with curative intent).
	
The record of the revised management plan post fluciclovine (¹⁸F) PET/CT scan in comparison to the pre-scan intended management plan.

Secondary Objectives
 
 1. To assess possible improvement in outcome of radical salvage treatment based on fluciclovine (¹⁸F) PET/CT being included in the assessment. 2. To assess the prostate specific antigen (PSA) threshold for positive lesion detection by fluciclovine (¹⁸F) PET/CT in BCR 3. To assess the safety of fluciclovine (¹⁸F) injection in patients undergoing PET/CT 4. 	
 1. The proportion of patients who have a sustained response to radical salvage therapy. 2. PSA levels in relation to scan positivity will be analysed to determine the optimal PSA threshold for detecting recurrent PCa by fluciclovine (¹⁸F) PET/CT. 3. Safety will be assessed from data on the occurrence of adverse events (AEs) and changes in clinical laboratory tests, vital signs, injection-site status, and physical examination findings from the time of administration of fluciclovine (¹⁸F) injection throughout the study period. 4. .

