7.4. Randomisation, blinding and code-breaking

All participants will receive fluciclovine (¹⁸F) injection.

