7.6. Fluciclovine (^{18}F) PET/CT

The PET/CT will be acquired on the highest quality scanner available in the participating institution. The participant will be required to fast for at least 4 hours prior to the scan, drinking only sips of water within 4 hours of the scan if needed for administration of medications, and not exercise from the day before the scan through to the time of the scan. The participant will be cannulated, preferably in the right arm, and receive one dose of fluciclovine (^{18}F) diluted up to 10 mL injected by intravenous push (5-10 seconds) via the cannula with arms down followed by $\geq 10\text{mL}$ flush [54]. The participant will be scanned in the supine position in the direction of mid-thigh to skull base, with the arms positioned overhead following the dose and flush. The uptake time should be 3 to 5 minutes with a goal of 4 minutes from the end of the dose. For the PET acquisition, participants will be imaged for approximately 25 minutes. For the CT parameters, a high-quality unenhanced CT will be employed. Further details on the PET/CT acquisition will be given in the Study Imaging Manual.

Vital signs, examination of the injection site and review of AE/SAEs will be performed immediately post scan and at 60(± 5) minutes, 90(± 5) minutes and 120(± 5) minutes post-injection. All images obtained during the trial will be retained for use in this research and may be used for future approved research studies.

Analysis

Image interpretation will be based on guidelines derived from an international fluciclovine (^{18}F) reader consensus meeting held in June 2014 [54]. All readers will undergo training in interpretation of fluciclovine (^{18}F) scans, and will have a training set available for reference.

Primary evaluation and reporting of the PET/CT scan will be site-based (as per standard of care). The clinical team should make the revised treatment decision on the site-based report.

The fluciclovine (^{18}F) PET/CT scan will be centrally reported at the end of the study, blinded to the original report. Copies of the fluciclovine (^{18}F) PET/CT will be transferred from the host site for this purpose. Copies of the original report will also be transferred, as this data will be used to determine inter-reader agreement.

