4 STUDY SUBJECTS

4.1 Analysis sets

The list of subjects to be included in each of the analysis set is to be agreed between the Syne qua non statistician and Blue Earth Diagnostics once all study data are available and prior to database lock.

Enrolled Set: All subjects who entered screening.

Safety Analysis Set (SAF): All subjects who have been included in the database and have been administered fluciclovine (¹⁸F) will be included in the Safety Analysis Set (SAF).

Full Analysis Set (FAS): All subjects enrolled who have had a fluciclovine (¹⁸F) PET/CT scan will be included in the Full Analysis Set (FAS).

Evaluable Analysis Set (EAS): All subjects from the FAS who have an intended treatment management plan completed and a revised management plan page completed will be included in the Evaluable Analysis Set (EAS).

Per Protocol Set (PPS): All subjects in the EAS without major significant deviation following review of the protocol deviation list.

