1 INTRODUCTION

This the second addendum to the final statistical analysis plan (SAP) Amendment 1 dated 10th October 2018, documenting additional analyses following database lock. Full details of the changes are detailed below.

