2 CHANGES TO THE FINAL SAP

2.1 Change 1

Section 5.4.2.1 Treatment response as assessed by change in PSA

The number, percentage and exact 95% CI of subjects having a treatment response, stable disease and disease progression, as assessed by change in PSA, will be presented for subjects in the FAS who had salvage therapy. The summary will include an overall summary and separate summaries for subjects who had therapy guided by fluciclovine and for subjects whose therapy was not guided by fluciclovine.

This additional table will be of the same format as *Table 14.2.2.1 Treatment Response Assessment as Assessed by PSA - by Disease Location*, with the categories "Overall", "Local Disease" and "Extra-prostatic disease", replaced with "Salvage Therapy – All", "Salvage Therapy Guided by Fluciclovine" and "Salvage Therapy Not Guided by Fluciclovine" respectively.

This description is considered sufficient and a shell is not required. The title will be "Table 14.2.2.5 Treatment Response Assessment as Assessed by PSA in Subjects with Salvage Therapy - by Guided by/Not Guided by Fluciclovine".

Subjects will be determined to have a therapy guided by fluciclovine if they have an agreed therapy which contains the text string "GUIDED BY FLUCICLOVINE".

Reason for the change

To assess possible improvement in outcome of radical salvage treatment based on 18F fluciclovine PET/CT being included in the assessment.

2.2 Change 2

Section 5.4.2.3 Summary of disease location in subjects who had a change in management plan from salvage therapy to non-salvage therapy

The number and percentage of subjects who had positive extra-prostatic findings and negative extra-prostatic findings will be presented for subjects who had a change in management plan from salvage therapy to non-salvage therapy.

Subjects who had a change in management plan from salvage therapy to non-salvage therapy will be identified where the change of management plan is "SALVAGE THERAPY TO NON-CURATIVE SYSTEMIC THERAPY".

Positive/negative extra-prostatic findings will be determined from the imaging results.

This description is considered sufficient and a shell is not required. The title will be "Table 14.2.2.6 Presence of Extra-prostatic Disease in Subjects with Change of Management Plan from Salvage Therapy to Non-salvage Therapy".

Date: 08MAR2019 Version: Addendum 2 Final ST/form/038/1

Blue Earth Diagnostics study no: BED004

Syne qua non study no: BLS14004

Reason for the change

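### SAP Addendum 2, Change 1 says the guided versus not-guided table assesses improvement from PET/CT, but both columns were scanned, so it can only describe outcome

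*SAP*

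**What the plan says.** SAP Addendum 2 describes itself as "documenting additional analyses following database lock". Its Change 1 extends SAP section 5.4.2.1 with a new Table 14.2.2.5. For full analysis set (FAS) patients who had salvage therapy, the table gives the number, percentage and exact 95% CI with PSA response, stable disease and progression. It has an overall column and "separate summaries for subjects who had therapy guided by fluciclovine and for subjects whose therapy was not guided by fluciclovine". A patient counts as guided if the agreed therapy contains the text string GUIDED BY FLUCICLOVINE.

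The reason given is "To assess possible improvement in outcome of radical salvage treatment based on 18F fluciclovine PET/CT being included in the assessment". This restates the first secondary objective in Protocol section 4, "To assess possible improvement in outcome of radical salvage treatment".

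Three other provisions matter:

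- Protocol 7.4: "All participants will receive fluciclovine" injection. There is no randomisation and no unscanned group.
- SAP 4.1: the FAS is "All subjects enrolled who have had a fluciclovine" PET/CT scan.
- Protocol 7.6: "The clinical team should make the revised treatment decision on the site-based report". The treatment choice therefore comes after the scan result.

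**The concern.** The stated purpose concerns the effect of having PET/CT in the work-up. The table compares two groups that both had it. Not guided does not mean that the scan was not used: a negative scan that supported the original plan also falls in that column.

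Membership of the two columns probably depends on the scan result. Boosting an area picked out by PET presupposes that PET showed something. The not-guided column is then likely to pool patients with negative scans and patients with positive scans for whom no guided option was agreed. If scan result is related to PSA response, the columns would differ even if guidance did nothing. Change 1 does not restrict or stratify the contrast by scan result and carries no caveat.

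At stake is what the report may say about this secondary objective. A difference between the columns, placed under that stated reason, invites a conclusion about improvement that the comparison cannot carry.

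**Working it through.** **Figures in the plan.** The documents give no sample size, power or effect size for this contrast. The only size calculation (Protocol 11.1, SAP 3.4) is for the primary proportion, and it reproduces: 1.96² × 0.20 × 0.80 / 0.06² = 170.7, so 171; 171 / 0.95 = 180. It gives no support to the guided versus not-guided comparison.

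**Is there a no-PET comparator?** Protocol 7.4 gives everyone the injection, and SAP 4.1 admits only scanned patients to the FAS. Both columns of Table 14.2.2.5 are drawn from the FAS. The number of unscanned patients in either column is therefore zero by definition.

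**Does guided depend on the scan result?** The plan table in SAP 5.4.1 lists six revised-plan options that contain the string. Four are boosts to areas identified by the scan (radiotherapy to the prostate bed, radiotherapy to bed and whole pelvis, cryotherapy, brachytherapy). Two are treatment plans guided by the scan (brachytherapy, HIFU). I assume that the agreed plan uses the same list. The boosts presuppose a finding; the two plan-guided options need not. The dependence is thus inferred from the option wording and is not stated as a rule.

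**Could scan result matter for outcome?** Protocol 3.3 reports that patients with negative choline scans did better than those with positive scans. That is a different tracer, and the outcomes were recurrence, disease and treatment-free survival rather than PSA response. It is a reason to expect that scan status is prognostic, not a measure of how much.

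**Size of the possible distortion (all inputs assumed).** Let

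- π = share of salvage patients with a positive scan: 40% to 70%
- g = share of positives who are guided: 30% to 80%; no negatives are guided
- rP, rN = response rates in scan-positive and scan-negative patients: 50% to 70%, differing by up to 20 points either way
- δ = true effect of guidance.

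The share of the not-guided column that is scan-positive is w = π(1 − g) / [π(1 − g) + (1 − π)], so 1 − w = (1 − π) / (1 − πg). The expected guided minus not-guided difference is

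D = δ + (1 − w)(rP − rN).

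With δ = 0:

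| π | g | 1 − w | D if rP − rN = −20 | D if rP − rN = +20 |
|---|---|---|---|---|
| 0.40 | 0.80 | 0.60/0.68 = 0.882 | −17.6 | +17.6 |
| 0.56 | 0.50 | 0.44/0.72 = 0.611 | −12.2 | +12.2 |
| 0.70 | 0.30 | 0.30/0.79 = 0.380 | −7.6 | +7.6 |

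D is zero when rP = rN. With δ = +10 points, the extremes are 10 − 17.6 = −7.6 and 10 + 17.6 = +27.6. The unrestricted table could therefore show a difference with no effect of guidance, or hide or reverse a real one.

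If the contrast is restricted to scan-positive patients, w = 1 and the second term vanishes. That removes the part due to scan result and nothing else.

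**The case against.** **No inference is planned.** Change 1 specifies counts, percentages and an exact CI per column, with no test, estimated difference, model or decision rule. This stands. A reader might infer that the plan builds in a false significance claim; it does not.

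**The timing is declared.** The addendum says openly that its analyses follow lock. A reader might infer an undisclosed post hoc analysis; the documents do not support that. The objective itself dates from the protocol, and only this split is new.

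**The objective has another analysis.** SAP 5.4.2.1 already reports PSA response in salvage patients, and also by disease location, treatment administered and plan change. It would be too strong to say that the secondary objective rests on Table 14.2.2.5 alone, or that location and treatment are ignored. They are not crossed with guidance, however, and 5.4.2.1 has no unscanned comparator either.

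**The wording and the lack of a control are inherited.** The stated reason nearly repeats the protocol's objective, including its hedge that improvement is only possible. The missing comparator follows from the single-arm design. This stands, but it does not make the new contrast a suitable answer.

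**The imbalance is not documented.** No data show that the columns differ in scan result, disease site or PSA. Imbalance in scan result is a plausible inference; for site and PSA it is weaker.

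**Restriction has limits.** Crossing guidance (2) by location (2) by the seven SAP PSA categories gives 28 cells. With the 85 patients of the interim analysis, and even if all were scan-positive salvage patients, that is about 3 per cell. Among scan-positive patients, guidance still reflects clinician and patient choice. Both points stand and shape the fix.

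**Conclusion.** The concern holds in a limited form. Table 14.2.2.5 is given a purpose that its contrast cannot serve, because PET/CT was part of the assessment in both columns. This follows from Protocol 7.4 and SAP 4.1 and needs no numerical assumption.

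That a difference may reflect scan result rather than guidance is probable but rests on the wording of the guided options. Its size is unknown. Over the assumed ranges, and with no effect of guidance, it runs from −17.6 to +17.6 points and includes zero. No single value in that range is an estimate of bias in this trial. The choline background might tempt a reader to conclude that the table will be biased against guidance; a different tracer and different outcomes do not establish the direction.

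The table may stay as a description. It should not be cited as evidence that PET/CT improved, or failed to improve, the outcome of salvage therapy.

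**What to change.** 1. In Addendum 2, Change 1, replace the stated reason with wording such as: *post hoc, descriptive; there is no no-PET comparator, so this table does not assess improvement*.
2. For each column, show scan result (positive or negative), disease location (local or extra-prostatic) and a summary of baseline PSA.
3. Present guided versus not guided within scan-positive salvage patients as a one-way display. Do not cross location with the seven PSA categories.
4. State that confounding by clinician and patient choice remains after this restriction.
5. Word the report's conclusion for this secondary objective as a description of outcome after salvage therapy.

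Scan result, location and baseline PSA are already used elsewhere in the SAP (5.4.1, 5.4.2.1, 5.4.2.2), so no new data are needed. The cost is a small reanalysis, the loss of the improvement wording for this table, and wider intervals. As an indication with assumed group sizes and 70% response in both groups, the 95% half-width for a difference is 1.96 × √(0.21/20 + 0.21/40) = 24.6 points for 20 versus 40 patients, and 32.8 points for 10 versus 30. The restricted display will be imprecise and should be presented as such.

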2 GENERAL PRINCIPLES

The analysis and statistical reporting will be conducted at Syne qua non using SAS version 9.2 or higher.

All listings will be based on all enrolled subjects unless specified otherwise. All tables will be presented by site and overall for the appropriate analysis population.

Descriptive summary statistics for continuous variables will include number of subjects (n), mean, standard deviation (SD), minimum, median, and maximum, unless specified otherwise. The precision of these summary statistics is defined in the table, figure and listing shells document.

Descriptive summary statistics for categorical variables will include frequency counts and percentages [n (%)]. Unless stated otherwise, the denominator for percentage calculations will be the number of subjects in the analysis set.

For treatment response baseline prostate specific antigen (PSA) is the most recent PSA measurement prior to salvage therapy for subjects who had salvage treatment and the most recent PSA measurement prior to the 18F-fluciclovine positron emission tomography/computerised tomography (PET/CT) for non-salvage subjects. If no PSA measurement is available just prior to salvage therapy, baseline will be defined as the most recent PSA measurement prior to fluciclovine (¹⁸F) scan. For all other variables, and for baseline PSA other than for treatment response, baseline is defined as the most recent value prior to fluciclovine (¹⁸F) administration.

In general, there will be no imputation of missing data, however where dates are partially missing dates may be imputed for calculation purposes, details are given under relevant section.

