5.4 Statistical Analysis

5.4.1 Primary Efficacy Analysis

The analysis of the primary outcome will be performed on the EAS as the primary analysis and will be repeated on the PPS as a secondary analysis. Comparisons between the original treatment plan and the revised treatment plan will be categorised as no change, major change or other change. The definitions of the change categories are listed below.

- No change: the original treatment plan is the same as the revised treatment plan
- Major change: the original treatment plan is not the same as the revised treatment plan and the grouping for the original treatment plan is not the same as the grouping for the revised treatment plan

These will be further split and presented according to the following categories:

- Salvage or Non-curative systemic therapy to Watchful waiting
- Salvage therapy to Non-curative systemic therapy
- Non-curative systemic therapy to Salvage therapy
- Alternative Major change
- Other change: the original treatment plan is not the same as the revised treatment plan but the grouping for the original treatment plan is the same as the grouping for the revised treatment plan

These will be further split and presented according to the following categories:

- Modified RT field plan
- Modified androgen-deprivation regimen
- Alternative Other change

Groupings of treatment plans are detailed in the following table:

Date: 10OCT2018 Version: Amendment 1 Final

Version: Amendment 1 Fina ST/form/010/6

Original Treatment Plan	Grouping for Original Tx Plan	Revised Treatment	Grouping for Revised Tx Plan
Was androgen deprivation therapy planned	Androgen Deprivation Therapy	Androgen deprivation therapy	Androgen deprivation therapy
		Watch and wait	Watch and wait
		Chemotherapy	Chemotherapy
Salvage radiotherapy to the prostate bed		Salvage radiotherapy to the prostate bed	
Salvage radiotherapy to the prostate bed, with boost to areas guided by conventional imaging	Salvage Radiotherapy	Salvage radiotherapy to the prostate bed, with boost to areas guided by conventional imaging	Salvage Radiotherapy
		Salvage radiotherapy to the prostate bed with boost to areas guided by fluciclovine (18F) PET/CT	
Salvage radiotherapy to the prostate bed and whole pelvis		Salvage radiotherapy to the prostate bed and whole pelvis	

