Salvage radiotherapy to the prostate bed and whole pelvis, with boost to areas guided by conventional imaging	Salvage Radiotherapy	Salvage radiotherapy to the prostate bed and whole pelvis, with boost to areas guided by conventional imaging	Salvage Radiotherapy
		Salvage radiotherapy to the prostate bed and whole pelvis with boost to areas guided by fluciclovine (18F) PET/CT	

Original Treatment Plan	Grouping for Original Tx Plan	Revised Treatment Plan	Grouping for Revised Tx Plan
Salvage cryotherapy		Salvage cryotherapy	
	Salvage Cryotherapy	Salvage cryotherapy with boost to areas guided by fluciclovine (18F) PET/CT	Salvage Cryotherapy
Salvage brachytherapy		Salvage brachytherapy	
	Salvage Brachytherapy	Salvage brachytherapy with boost to areas guided by fluciclovine (18F) PET/CT	Salvage Brachytherapy
		Salvage brachytherapy with treatment plan guided by fluciclovine (18F) PET/CT	
Salvage HIFU		Salvage HIFU	
	Salvage HIFU	Salvage HIFU with treatment plan guided by fluciclovine (18F) PET/CT	Salvage HIFU
Salvage prostatectomy		Salvage prostatectomy	
	Salvage Prostatectomy	Salvage prostatectomy with targeted resection / sampling of fluciclovine (18F) positive areas outside conventional surgical field	Salvage Prostatectomy
Salvage prostatectomy and limited lymph node dissection		Salvage prostatectomy and limited lymph node dissection	

Original Treatment Plan	Grouping for Original Tx Plan	Revised Treatment Plan	Grouping for Revised Tx Plan
		Salvage prostatectomy and limited lymph node dissection with targeted resection / sampling of fluciclovine (18F) positive areas outside surgical field	
Salvage prostatectomy and extended lymph node dissection (including internal and external iliac, and obturator nodes)		Salvage prostatectomy and extended lymph node dissection (including internal and external iliac, and obturator nodes)	
		Salvage prostatectomy and extended lymph node dissection (including internal and external iliac, and obturator nodes) with targeted resection / sampling of fluciclovine (18F) positive areas outside surgical field	
		Targeted salvage treatment of fluciclovine (18F) positive extra-pelvic / bony areas	Targeted salvage treatment
		Other	Other

The classification and sub-classification of change in treatment management plan will be agreed prior to data base lock.

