The number, percentage and exact 95% CI of subjects with and without a change in management plan after the fluciclovine (18F) scan results become available will be presented. In addition, the number and percentage of subjects with changes categorised as major or other will be presented. These summaries will be repeated separately for subjects with a positive and a negative fluciclovine (18F) scan and for subjects without prostatectomy and with prostatectomy.

Date: 10OCT2018 Version: Amendment 1 Final Page 17 of 22

The number, percentage and 95% CI of subjects who agreed to the revised management plan after fluciclovine (¹⁸F) scan results become available will be presented.

Details of the intended management plan, revised management plan and agreed management plan will be listed.

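### Table 14.2.2.6 in SAP Addendum 2 is described as covering plan changes from salvage to non-salvage therapy, but its selection rule admits only moves to non-curative systemic therapy

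*SAP*

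**What the plan says.** SAP Addendum 2, section 2.2 (Change 2), adds Table 14.2.2.6. The new section is headed "Summary of disease location in subjects who had a change in management plan from salvage therapy to non-salvage therapy" and the table is titled "Presence of Extra-prostatic Disease in Subjects with Change of Management Plan from Salvage Therapy to Non-salvage Therapy". The body text describes the population in the same terms. None of the three narrows it to a particular kind of non-salvage plan.

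The selection rule follows: "Subjects who had a change in management plan from salvage therapy to non-salvage therapy will be identified where the change of management plan is" a single code, salvage therapy to non-curative systemic therapy. The addendum says that no table shell is needed, and it specifies no footnote.

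SAP 5.4.1 divides major changes into four categories. The selected code is one of them. Another is "Salvage or Non-curative systemic therapy to Watchful waiting", and a residual one is "Alternative Major change". In the grouping table of the same section, watch and wait is a possible revised plan with its own grouping.

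**The concern.** The label and the selection name different groups. A patient planned for salvage treatment and moved to watchful waiting after the scan has gone from salvage to non-salvage. That patient carries another code, so the rule cannot pick the patient up.

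The table is meant to show how often patients taken off salvage had extra-prostatic findings. If watchful-waiting patients exist and their findings differ from those of patients moved to systemic therapy, the printed percentage does not describe the group in the title. A reader of the addendum can see the restriction. A reader of the table alone cannot, unless a footnote is added.

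**Working it through.** **Inputs.** The population comes from the heading, text and title of Change 2; the rule comes from the same section; the categories come from SAP 5.4.1. There is no planned figure to reproduce.

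**Category check.**

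| Major-change category (SAP 5.4.1) | Can it hold salvage to non-salvage moves? | Selected for Table 14.2.2.6? |
|---|---|---|
| Salvage to non-curative systemic therapy | Yes | Yes |
| "Salvage or Non-curative systemic therapy to Watchful waiting" | Yes, for its salvage-origin patients only | No |
| Non-curative systemic therapy to salvage | No | No |
| "Alternative Major change" | Possibly; the category is not defined | No |

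The second row shows the mismatch. It also shows that adding the watchful-waiting code would not repair it, because that code pools two origins and would bring in patients who were never planned for salvage.

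The fourth row is uncertain. A move from a salvage plan to "Targeted salvage treatment of fluciclovine (18F) positive extra-pelvic / bony areas" changes grouping and matches none of the three named categories, so it could fall here while still being salvage. The residual category cannot be assumed to contain any salvage to non-salvage move.

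**Size.** Let the table print k positive out of n selected. Let m be the number of patients who fit the description but are not selected, with j of them positive (0 ≤ j ≤ m).

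- Printed share: k/n.
- Full share: (k + j)/(n + m), which lies between k/(n + m) and (k + m)/(n + m).
- Difference, full minus printed: (k + j)/(n + m) − k/n = (nj − mk)/[n(n + m)] = [m/(n + m)] × (j/m − k/n) for m > 0.
- The last bracket is a difference of two proportions and lies between −1 and 1, so the absolute difference is at most m/(n + m).

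The difference is zero if m = 0 or if the two positivity rates are equal. A single omitted patient moves the share by at most 1/(n + 1).

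**What the documents give for n, m and k.** Nothing. The one count of plan changes, more than 45 in the first 85 evaluable patients (Protocol 11.3), is not split by destination. On the same analysis set, the watchful-waiting part of m cannot exceed the count in the pooled watchful-waiting category that SAP 5.4.1 already presents.

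**The case against.** The strongest reply is that the addendum defines its own term. The rule stands next to the description and is unambiguous to a programmer. SAP 5.4.1 also sets watchful waiting against therapy, so non-salvage therapy could mean systemic therapy only. The restriction may have been deliberate, and the stated reason for Change 2, which might settle this, is not in the available text. The addendum was written after database lock, so its authors could have known which codes were populated.

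Part of this stands. The narrow reading is possible, and intent cannot be established. But it is not how the documents generally use the word. Protocol 7.7 divides follow-up into radical salvage therapy and non-salvage management. SAP section 2 sets the PSA baseline "prior to salvage therapy for subjects who had salvage treatment" and calls the rest non-salvage; there, therapy and treatment are interchangeable. SAP 5.4.2.1 splits response the same two ways, although by treatment received and not by plan change. Even if the narrow reading was meant, the title remains wider than the group counted, and the SAP already has an exact term for that group.

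A reader might infer that patients have in fact been dropped, or that the printed percentage is biased in a known direction. The documents support neither: m may be zero, and no positivity rate is given for either group.

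**Conclusion.** The rule as written cannot deliver the population that the heading, text and title name. That rests on the wording alone. Whether the selection or the label is at fault depends on intent, which the documents do not show.

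The consequence is small: one descriptive table, added after lock, with no test attached and no bearing on the primary endpoint. The numerical effect is unknown, may be nil, and is bounded by m/(n + m).

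No other table described in the available SAP text gives extra-prostatic status for patients moved from salvage to watchful waiting. SAP 5.4.1 repeats the change summaries by scan result but not by lesion location. The table shells are a separate document and parts of the SAP are not available, so this cannot be stated more strongly. The information is not lost: SAP 5.4.1 says "Details of the intended management plan, revised management plan and agreed management plan will be listed", and SAP 5.4.2.2 lists the imaging results, so the figure could be rebuilt by hand.

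**What to change.** Make label and selection agree, in one of two ways.

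- **A. If the broad population was intended:** select patients whose original plan contains a salvage grouping and whose revised plan contains no salvage grouping. Count the targeted salvage grouping as salvage, and check entries under Other for salvage content. Do not treat androgen deprivation given alongside a salvage treatment as non-salvage; it has its own item and grouping in SAP 5.4.1 and may accompany salvage radiotherapy. Show watchful waiting as its own row.
- **B. If the restriction was intended:** change the heading, text and title to Salvage Therapy to Non-curative Systemic Therapy. A separate row for salvage to watchful waiting would be informative but is optional.

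Option A costs a revised selection and an added row in one table, a check of the Other entries, and matching addendum wording, all from plan fields already collected. Option B costs wording changes in three places; the optional row would also require splitting the pooled watchful-waiting code by original plan. Neither option reopens the SAP 5.4.1 categories.
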